5.8.1 Procedures for discontinuation of a patient from investigational products

A patient that decides to discontinue the investigational products will always be asked about the reason(s) and the presence of any AEs. If possible, they will be seen and assessed according to procedures as in Visit 11 and the eCRF will be completed. AEs will be followed up (See Sections 6.4.3 and 6.4.4); diaries and the investigational products should be returned by the patient.

If a patient is withdrawn from study, see Section 5.9.

5.9 Withdrawal from study

Patients are at any time free to withdraw from study (investigational products and assessments), without prejudice to further treatment (withdrawal of consent). Such patients will always be asked about the reason(s) and the presence of any AEs. If possible, they will be seen and assessed according to procedures as in Visit 11 and the eCRF will be completed. AEs will be followed up (See Sections 6.4.3 and 6.4.4); diaries and the investigational products should be returned by the patient.

A patient withdrawn from the study will not be replaced.

6. COLLECTION OF STUDY VARIABLES

6.1 Recording of data

The Web Based Data Capture (WBDC) system (Rave from Medidata) will be used for data collection and query handling. Trained study centre personnel will be responsible for entering data specified in the protocol into the WBDC system and according to the eCRF Instructions. The investigator will ensure that data are recorded on the eCRFs as specified in the study protocol and in accordance with the instructions provided.

The investigator ensures the accuracy, completeness and timelines of the data recorded and of the provision of answers to data queries according to the Clinical Study Agreement (CSA). The investigator will sign the completed eCRFs. A copy of the completed eCRFs will be archived at the study centre.

6.2 Data collection and enrolment

The following data will be collected and recorded in the appropriate sections of the eCRF (refer to the Study Plan, Section 3.1).

- Date of signed informed consent.
- Inclusion and exclusion criteria.
- Demography: Date of birth, sex and race.
- Laboratory assessments.
- Medical history, including information about: general medical history, surgical history, lifestyle (tobacco, alcohol, exercise), family history, specific disease history.
- Physical examination, see Section 6.4.6.
- Vital signs (blood pressure, pulse rate), see Section 6.4.8.
- Height, weight and waist circumference, see Section 6.4.8.
- A 12-lead ECG, see Section 6.4.7.
- Prior and concomitant medication.

6.2.1 Follow-up procedures

Which follow-up procedures and when to be assessed are explained in the Study Plan, Table 1. Randomised patients who do not complete the entire study should complete the procedures described for Visit 11.

Unresolved AEs will be followed up according to Section 6.4.3.

6.3 Efficacy

The baseline is defined as the assessment at randomisation visit (Visit 3).

Self-monitoring of plasma glucose should be done in order to reduce risk of prolonged periods of undetected hyperglycaemia or to confirm hypoglycaemia. Patients will be asked to do self-monitoring of plasma glucose using glucometers provided by AstraZeneca. The patients will receive instruction on the use of the glucometer, according to the manufacturer's instruction.

6.3.1 Efficacy laboratory variables

The laboratory variables that will be measured to assess efficacy, and at which visits to be measured, are shown in Table 2. These variables will be assessed at a central laboratory. For information on methods of collection, assessment, labelling, storage and shipment of samples, see the Laboratory Manual.

Visit number	S	1	2	3	4	5	6	7	8	9	10	11
Study Week	-6	-4	-2	0	3	6	9	12	24	32	40	52
HbA _{1c}	Х			Х				Х	Х	Х	Х	Х
FPG ^a				Х	Х	Х	Х	Х	Х	Х	Х	Х
Insulin ^a				Х					Х			Х
TC, LDL-C, HDL-C, TG ^a				Х					Х			Х

Table 2Efficacy laboratory variables

a. Fasting

Patients should be instructed to abstain from all food for 8 hours prior to each visit; drinking water is allowed. The investigational products should not be taken in the morning prior to any of the visits, but acceptable concomitant medications can be taken with water only.

Fasting plasma glucose will for the duration of the study be measured at the study center, using a glucose analyser (HemoCue[®]) provided by AstraZeneca. For information on methods for collection and assessment of samples, see the manual provided by the manufacturer.

6.4 Safety

The Principal investigator is responsible for ensuring that all staff involved in the study is familiar with the content of this section.

6.4.1 Definition of adverse events

An Adverse Event (AE) is the development of an undesirable medical condition or the deterioration of a pre-existing medical condition following or during exposure to a pharmaceutical product, whether or not considered causally related to the product. An
undesirable medical condition can be symptoms (eg, nausea, chest pain), signs (eg, tachycardia, enlarged liver) or the abnormal results of an investigation (eg, laboratory findings, electrocardiogram). In clinical studies, an AE can include an undesirable medical condition occurring at any time, including run-in or washout periods, even if no study treatment has been administered.

The term AE is used to include both serious and non-serious AEs.

6.4.2 Definitions of serious adverse event

A serious adverse event (SAE) is an AE occurring during any study phase (ie, enrolment, lead-in, titration and maintenance treatment periods), that fulfils one or more of the following criteria:

- Results in death
- Is immediately life-threatening
- Requires in-patient hospitalisation or prolongation of existing hospitalisation
- Results in persistent or significant disability or incapacity
- Is a congenital abnormality or birth defect
- Is an important medical event that may jeopardise the patient or may require medical intervention to prevent one of the outcomes listed above
- Cancer
- Drug dependency/abuse

For further guidance on the definition of a SAE, see Appendix B.

SAEs related to bone fracture, skin lesions, infection, lymphocytopenia, thrombocytopenia and symptomatic hand and foot oedema should be given special attention. Regarding bone fractures is should include both non-serious and serious events. Supplemental paper CRF are to be completed by the study investigators for these specific AEs/SAEs.

For the purposes of regulatory reporting, the following events/medical conditions should be reported as described in Section 6.4.4, in the same timelines as SAEs regardless of whether the event/medical condition is classified as serious or non-serious:

- Pancreatitis
- Opportunistic infections (eg, tuberculosis, Herpes zoster, cytomegalovirus, Pneumocystis jirovecii, etc)

Serum AST or ALT greater than or equal to 3 times ULN concomitant with serum total bilirubin greater than 2 times ULN or evidence of jaundice.

6.4.3 Recording of adverse events

6.4.3.1 Time period for collection of adverse events

Adverse Events will be collected from randomization at Visit 3 throughout the double-blind treatment period until and including the last contact, Visit 11.

Serious Adverse Events will be collected from the signature of informed consent throughout the treatment period until and including the last contact, Visit 11.

6.4.3.2 Adverse event dictionary

The latest version of the AE dictionary, Medical Dictionary for Regulatory Activities (MedDRA), will be used for the classification and analysis of AEs entered in the study database. For regulatory reporting, SAEs will be processed at the Bristol-Myers Squibb Pharmacovigilance database and coded using MedDRA.

6.4.3.3 Variables

The following variables will be collect for each AE;

- AE (verbatim)
- Date when AE started and stopped
- Maximum intensity, mild, moderate, severe, very severe
- Whether AE is serious or not
- Investigator causality rating against the investigational products (yes or no)
- Action taken with regard to investigational product
- AE caused patient's withdrawal from study (yes or no)
- Outcome

In addition, the following variables will be collected for SAEs:

- Date AE met criteria for SAE
- Date investigator became aware of SAE
- AE is serious due to
- Date of hospitalisation
- Date of discharge
- Probable cause of death
- Date of death

Revised Clinical Study Protocol Drug Substance Saxagliptin Study Code **D1680L00002** Edition Number 4.0 Date

- Autopsy performed
- Causality assessment in relation to Study procedure(s)
- Causality assessment in relation to Other medication
- Description of AE

If the intensity of an AE changes, only the maximum intensity of the event will be recorded.

Intensity is defined as one of the following:

- Mild: Awareness of event, but easily tolerated
- Moderate: Discomfort enough to cause some interference with usual activity
- Severe: Inability to carry out usual activity
- Very severe: Debilitating, significantly incapacitates patient despite symptomatic therapy

It is important to distinguish between serious and severe AEs. Severity is a measure of intensity whereas seriousness is defined by the criteria in Section 6.4.2. An AE of severe intensity need not necessarily be considered serious. For example, nausea that persists for several hours may be considered severe nausea, but not a SAE. On the other hand, a stroke that results in only a limited degree of disability may be considered a mild stroke but would be a SAE.

6.4.3.4 Causality collection

The investigator will assess causal relationship between investigational products and each AE, and answer "yes" or "no" to the question "Do you consider that there is a reasonable possibility that the event may have been caused by the investigational products?" If there is any valid reason, even if undetermined or untested, for suspecting a possible cause-and-effect relationship between the investigational products and the occurrence of the AE, then this should be answered "yes". Otherwise, if no valid reason exists for suggesting a possible relationship, then this should be answered "no". If more than one AE is identified, a causality assessment must be made for each AE.

For SAEs causal relationship will also be assessed for other medication and study procedures. Note that for SAEs that could be associated with any study procedure the causal relationship is implied as "yes".

A guide to the interpretation of the causality question is found in Appendix B.

6.4.3.5 Adverse events based on signs and symptoms

All AEs spontaneously reported by the patient or reported in response to the open question from the study personnel: "Have you had any health problems since the previous visit?", or revealed by observation will be collected and recorded in the eCRF. When collecting AEs,

Revised Clinical Study Protocol Drug Substance Saxagliptin Study Code **D1680L00002** Edition Number 4.0 Date

the recording of diagnoses is preferred (when possible) to recording a list of signs and symptoms. However, if a diagnosis is known and there are other signs or symptoms that are not generally part of the diagnosis, the diagnosis and each sign or symptom will be recorded separately.

6.4.3.6 Adverse events based on examinations and tests

The results from protocol mandated laboratory tests and vital signs will be summarised in the clinical study report (CSR). Deterioration as compared to baseline in protocol-mandated laboratory values, vital signs and other safety variables should therefore only be reported as AEs if they fulfil any of the SAE criteria or are the reason for discontinuation of treatment with the investigational products or meet the requirements for regulatory reporting, as described in Section 6.4.2.

If deterioration in a laboratory value/vital sign is associated with clinical signs and symptoms, the sign or symptom will be reported as an AE and the associated laboratory result/vital sign will be considered as additional information. Wherever possible, the reporting investigator uses the clinical, rather than the laboratory term (eg, anaemia versus low haemoglobin value). In the absence of clinical signs or symptoms, clinically relevant deteriorations in non-mandated parameters should be reported as AE(s).

Deterioration of a laboratory value, which is unequivocally due to disease progression, should not be reported as an AE/SAE.

Any new or aggravated clinically relevant abnormal medical finding at a physical examination, as compared with the baseline assessment, will be reported as an AE.

6.4.3.7 Disease progression

Disease progression can be considered as a worsening of a patient's condition attributable to the disease for which the investigational products is being studied. It may be an increase in the severity of the disease under study and/or increases in the symptoms of the disease. Events, which are unequivocally due to disease progression, should not be reported as an AE during the study.

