6.4.4 Reporting of serious adverse events

All SAEs have to be reported, whether or not considered causally related to the investigational products, or to the study procedure(s). All SAEs will be recorded in the eCRF.

If any SAE occurs in the course of the study, then investigators or other site personnel inform appropriate AstraZeneca representatives within one day, ie, immediately but **no later than the end of the next business day** of when he or she becomes aware of it.

The designated AstraZeneca representative works with the investigator to ensure that all relevant information is provided to Bristol-Myers Squibb Global Pharmacovigilance & Epidemiology **within one calendar day** of initial receipt for all SAEs. The AstraZeneca representative will notify the appropriate Bristol-Myers Squibb Pharmacovigilance contact to ensure regulatory compliance.

For fatal or life-threatening AEs where important or relevant information is missing, active follow-up is undertaken immediately. Investigators or other site personnel inform AstraZeneca representatives of any follow-up information on a previously reported SAE within one calendar day, ie, immediately but **no later than the end of the next business day** of when he or she becomes aware of it.

The reference document for definition of expectedness/listedness is the Investigator Brochure for the investigational product, and the EU Summary of Product Characteristics (SPC) for the active comparator product (including any AstraZeneca comparator).

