- Consistency with known drug profile. Was the AE consistent with the previous knowledge of the suspect drug (pharmacology and toxicology) or drugs of the same pharmacological class? OR could the AE be anticipated from its pharmacological properties?
- Dechallenge experience. Did the AE resolve or improve on stopping or reducing the dose of the suspect drug?
- No alternative cause. The AE cannot be reasonably explained by another aetiology such as the underlying disease, other drugs, other host or environmental factors.
- Rechallenge experience. Did the AE reoccur if the suspected drug was reintroduced after having been stopped? AstraZeneca would not normally recommend or support a rechallenge.
- Laboratory tests. A specific laboratory investigation (if performed) has confirmed the relationship?

A "reasonable possibility" could be considered to exist for an AE where one or more of these factors exist.

In contrast, there would not be a "reasonable possibility" of causality if none of the above criteria apply or where there is evidence of exposure and a reasonable time course but any dechallenge (if performed) is negative or ambiguous or there is another more likely cause of the AE.

In difficult cases, other factors could be considered such as:

- Is this a recognised feature of overdose of the drug?
- Is there a known mechanism?

Ambiguous cases should be considered as being a "reasonable possibility" of a causal relationship unless further evidence becomes available to refute this. Causal relationship in cases where the disease under study has deteriorated due to lack of effect should be classified as no reasonable possibility.

Clinical Study Protocol Appendix C				
Drug Substance	Saxagliptin			
Study Code	D1680L00002			
Edition Number	1			
Date				

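### The disease-progression exemption from adverse-event reporting has no override for serious events, and the protocol does not say how it ranks against the rule that all SAEs are reported

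*Protocol*

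**What the plan says.** Two passages exempt disease progression from reporting.

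- Protocol 6.4.3.7: "Events, which are unequivocally due to disease progression, should not be reported as an AE during the study". The section describes progression broadly: "It may be an increase in the severity of the disease under study and/or increases in the symptoms of the disease". The disease under study is type 2 diabetes, so worsening hyperglycaemia fits.
- Protocol 6.4.3.6, third paragraph: "Deterioration of a laboratory value, which is unequivocally due to disease progression, should not be reported as an AE/SAE".

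Other passages point towards reporting.

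- 6.4.1 includes in the AE definition "the deterioration of a pre-existing medical condition following or during exposure to a pharmaceutical product, whether or not considered causally related to the product".
- 6.4.2 lists among the SAE criteria: "Requires in-patient hospitalisation or prolongation of existing hospitalisation".
- 6.4.4: "All SAEs have to be reported, whether or not considered causally related to the investigational products".
- 6.4.3.6, first paragraph, says that deteriorations in protocol-mandated laboratory values should "only be reported as AEs if they fulfil any of the SAE criteria or are the reason for discontinuation of treatment", or if they fall under the special reporting list in 6.4.2.

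Section 6.4.3.10 keeps hypoglycaemic events out of the ordinary AE section, but sends any that meet the SAE definition to the SAE section.

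**The concern.** In a comparison of two glucose-lowering regimens, serious hyperglycaemia is the harm to expect where control fails. The protocol itself foresees such cases. Section 1.4 treats overt hyperglycaemia as a safety and tolerability matter, and criterion 1 of Section 5.8 allows for admissions whose main reason is glycaemic control. Section 3.2.3 expects secondary failure to be more frequent on a sulphonylurea, so such events need not be equally common in the two arms.

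If one site files an admission for worsening diabetes as an SAE and another leaves it out as progression, the SAE table mixes two rules and some admissions never reach safety reporting. The same uncertainty affects whether a stop for high FPG or HbA1c is entered as an AE leading to discontinuation. Section 11.2.2 then uses SAE and DAE status to decide which AEs go to expert review. Section 12.4 says there is no data monitoring committee, so complete site reporting matters more.

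**Working it through.** The protocol gives no figure on this point, so the check is a reading of the rules against two cases.

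**Case A: hospital admission for worsening hyperglycaemia, which the site considers clear-cut progression.**

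1. Under 6.4.1 it is an AE, being deterioration of a pre-existing condition. That definition has no exception for the disease under study.
2. Under 6.4.2 it is serious, because the patient was admitted. Again there is no exception.
3. Under 6.4.4 it must be reported.
4. Under 6.4.3.7 it must not be reported as an AE. The clause has no exception for seriousness.

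Steps 3 and 4 give opposite instructions, and no section says which prevails. Nor does the protocol give a criterion for when progression is unequivocal, so that judgement is left to the site.

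**Case B: a stop under criteria 5 to 8 of Section 5.8 (confirmed high FPG, or HbA1c of 8.0% or more).**

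1. FPG and HbA1c are protocol-mandated laboratory values (Table 2).
2. If the value has worsened from baseline and is why treatment was stopped, the first paragraph of 6.4.3.6 makes it reportable as an AE.
3. If the worsening is judged to be unequivocal progression, the third paragraph of the same section says it is not reported, as AE or SAE.
4. Section 1.4 calls these lack-of-efficacy criteria. Section 5.8 lists AE-based safety reasons as a separate ground for stopping, and the sensitivity analysis in 12.2.1 separates glycaemic-control terminations from others. These passages suggest that such stops were not meant as AEs, but 6.4.3.6 does not say so.

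Not every stop of this kind reaches step 2. Entry allows HbA1c up to 9.0%, so a patient stopped at 8.0% or more may not have deteriorated from baseline.

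**Comparison within the document.** The hypoglycaemia exemption in 6.4.3.10 has an SAE override and the progression exemption has none. As written, serious hypoglycaemia is always reportable, while serious hyperglycaemia attributed to progression may not be.

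**Reach.** Section 12 counts any patient who does not complete 52 weeks as a non-responder, however the stop is coded, so the primary endpoint is unaffected. The key secondary endpoint uses hypoglycaemic events collected in their own eCRF module, so it is unaffected too.

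**The case against.** The strongest reply is that the passages can be read together. The first paragraph of 6.4.3.6 sets a general rule and its third paragraph removes a subset. An SAE is a kind of AE, so an event exempt as an AE falls outside the all-SAEs rule. That reading is available, but the protocol does not state it. Section 6.4.3.7 governs what is reported, not what an AE is, so under 6.4.1 and 6.4.2 the event remains an AE and an SAE. Moreover, if the reading is right, the result is that a serious hyperglycaemic event attributed to progression goes unreported. The gap then exists by rule and not only by inconsistency.

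Other parts of the reply stand, and they rule out several stronger conclusions that a reader might draw.

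- *That serious hyperglycaemia in general is kept off the lists.* The exemption covers only unequivocal progression. Hyperglycaemia from another cause, such as intercurrent illness or non-compliance, stays reportable.
- *That Appendix B contradicts the exemption outright.* It says "Causal relationship in cases where the disease under study has deteriorated due to lack of effect should be classified as no reasonable possibility", which implies that some such cases are reported. But deterioration from lack of effect is not the same as unequivocal progression, so this is only indirect support.
- *That the safety comparison is shown to be biased.* Treatment is double-blind and double-dummy, so differences between sites in reading the rules are not tied to arm by design. Omissions could be unequal if glycaemic failure is unequal, but nothing in the documents establishes that they would be. Central FPG and HbA1c are also collected independently of AE coding.
- *That the DAE rate would shift by a known amount.* The protocol states no rate of glycaemic stops. Its 10% drop-out assumption in 12.3 concerns reasons not related to glycaemic control, so any figure would be invented.

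**Conclusion.** The concern holds in a limited form. The progression exemption in 6.4.3.6 and 6.4.3.7 has no override for serious events and no stated rank against 6.4.2, 6.4.4 and the first paragraph of 6.4.3.6. A site following 6.4.3.7 as written may leave off the SAE list a serious hyperglycaemic event that it considers progression, and sites may differ on whether a glycaemic stop is a DAE. The consequence lies in the SAE and DAE tables and in safety reporting, and neither confirmatory test changes.

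The size cannot be computed from the documents. It depends on how many glycaemic events are serious or lead to stopping, and how often sites call them unequivocal progression. The conclusion assumes only that worsening type 2 diabetes counts as disease progression in this trial, which follows from the description in 6.4.3.7. Because AE reporting rules are set in the protocol, this is not a matter left to a statistical analysis plan. The point is worth correcting, chiefly for the serious events.

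**What to change.** 1. In 6.4.3.6 and 6.4.3.7, state that the disease-progression exemption does not apply to any event or laboratory deterioration that meets an SAE criterion or is on the special reporting list in 6.4.2. This mirrors the override already written in 6.4.3.10.
2. Reconcile the exemption with the reason-for-discontinuation clause in 6.4.3.6. State once how stops under criteria 5 to 8 of Section 5.8 are recorded, so that every site does the same. The rule should agree with their description as lack-of-efficacy stops in 1.4 and with the glycaemic-control classification used in 12.2.1.

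The stopping criteria themselves need no change. The cost is a few sentences in the protocol and eCRF instructions, a reminder to sites and slightly more SAE reports. No new data are needed.
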